9.1.1. Adverse Events of Special Interest

Adverse events of special interest (AESI) are the adverse events deemed related to VGX-3100/placebo delivered with CELLECTRATM 5PSP that require expedited communication from the Site to the Sponsor and meet any of the following criteria:

- Grade 3 or greater persistent administration site erythema, and/or induration recorded ≥ 2 hours immediately after Study Treatment
- Grade 4 or greater persistent administration site pain, tenderness recorded ≥ 2 hours immediately after Study Treatment
- Grade 3 or greater fever
- Grade 3 or greater systemic symptoms, including generalized pruritus

An AE summary table will include numbers and percentages of subjects experiencing at least one AESI by dose number, SOC and PT.

9.1.2. Incidence of Adverse Events

For the adverse events with onset date within 28 days after any dose, the frequency of SOC and PT events will be compared between study arms with risk differences and 95% confidence intervals, using the method of Miettinen and Nurminen [5]. As this analysis will use many event categories and produce many confidence intervals, caution should be exercised when interpreting these confidence intervals.

A similar analysis will be provided for adverse events within 7 days after any dose and for adverse events during the study after any dose.

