3.2.2. Secondary Endpoints

The secondary endpoints of this study are:

- 1. a. Incidence and severity of local and systemic events for 7 and 28 days following each investigational treatment and for the duration of the study (through Week 88 visit)
 - b. Incidence and severity of all adverse events including SAEs, SUSAR, UADE and other unexpected AEs for the duration of the study (through Week 88 visit)
- 2. Proportion of subjects with no evidence of cervical HSIL on histology (i.e. biopsies or excisional treatment) at Week 36 visit
- 3. Proportion of subjects with no evidence of HPV-16 and/or HPV-18 in cervical samples by type specific HPV testing at Week 36 visit
- 4. Proportion of subjects with no evidence of Low grade squamous intraepithelial lesion (LSIL) or HSIL (i.e. no evidence of CIN1, CIN2 or CIN3) on histology (i.e. biopsies or excisional treatment) at Week 36 visit

- 5. Proportion of subjects with no evidence of LSIL or HSIL (i.e. no evidence of CIN1, CIN2 or CIN3 on biopsies or excisional treatment) on histology (i.e. biopsies or excisional treatment) and no evidence of HPV-16 and/or HPV-18 by type specific HPV testing at Week 36 visit
- 6. Proportion of subjects with no progression of cervical HSIL to cervical carcinoma from baseline on histology (i.e. biopsies or excisional treatment) at Week 36 visit
- 7. Proportion of subjects who have cleared HPV-16 and/or HPV-18 on specimens from non-cervical anatomic locations (oropharynx, vagina and intra-anal) at Week 36 Visit
- 8. a. Levels of serum anti-HPV-16 and anti-HPV-18 antibody concentrations at Week 15 and 36 visits
 - b. Interferon-γ ELISpot response magnitudes at baseline, Weeks 15 and 36 visits
 - c. Flow Cytometry response magnitudes at baseline and Week 15 visits

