9.1. Adverse Events

A pretreatment event is defined as any event that occurs prior to administration of any study treatment; it does not necessarily have to have a causal relationship with study participation. A treatment emergent adverse event (TEAE) is defined as any event temporally associated with the use of a product whether or not considered related to the use of the product. Adverse event (AE) verbatim reported terms will be coded by SOC and PT using the latest version of MedDRA.

For the purpose of inclusion in AE summaries/analyses, incomplete start and stop dates will be imputed as follows:

Missing start dates will be handled as follows (where UK, UKN and UNKN indicate unknown or missing day, month and year respectively):

- UK-MMM-YYYY: if MMM and YYYY are the same as that of 1st dose, then impute to same date as 1st dose; otherwise impute to 01-MMM-YYYY;
- DD-UNK-YYYY; if DD and YYYY are the same as that of 1st dose, then impute to same date as 1st dose; otherwise impute to DD-JAN-YYYY;
- DD-MMM-UNKN; if DD and MMM are the same as that of 1st dose, then impute to same date as 1st dose; otherwise impute to DD-MMM-YOSCR, where YOSCR is year subject was initially screened;
- UK-UKN-YYYY: if YYYY is the same as that of 1st dose, then impute to same date as 1st dose; otherwise impute to impute to 01-JAN-YYYY;
- UK-MMM-UNKN: if MMM is the same as that of 1st dose, then impute to same date as 1st dose; otherwise impute to 01-MMM-YOSCR, where YOSCR is year subject was initially screened;
- DD-UNK-UNKN: if DD is the same as that of 1st dose, then impute to same date as 1st dose; otherwise impute to impute to DD-JAN-YOSCR, where YOSCR is year subject was initially screened;
- UK-UKN- UNKN: impute to date of subject's 1st dose.

If the imputed start date is after the raw stop date, then the imputed start date will be set as the same as the stop date.

Missing stop dates will be handled as follows (where UK, UKN and UNKN indicate unknown or missing day, month and year respectively):

- UK-MMM-YYYY: impute to the last day of the month;
- DD-UNK-YYYY: impute to DD-DEC-YYYY;
- DD-MMM-UNKN: impute to DD-MMM-YOLV, where YOLV is year of subject's last study visit;
- UK-UKN-YYYY: impute to 31-DEC-YYYY;
- UK-MMM-UNKN: impute to LD-MMM-YOLV, where LD is the last day of MMM and YOLV is year of subject's last study visit;
- DD-UNK-UNKN: impute to DD-DEC-YOLV, where YOLV is year of subject's last study visit;

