- UK-UKN- UNKN: impute to day of subject's last study visit.

If the imputed stop date is before the raw or imputed start date, then the imputed stop date will be set as the same as the start date.

AE duration will be calculated as (Stop Date – Start Date) + 1.

AE summary tables will include numbers and percentages of subjects experiencing at least one event by treatment arm. The following is a list of AE summary tables to be generated:

- Overview of AE, AE with onset within 28 days/7 days after study treatment
- TEAEs, TEAEs with onset within 28 days/7 days after study treatment by SOC and PT
- TEAEs, TEAEs with onset within 28 days/7 days after study treatment by Dose Number, SOC and PT
- TEAEs, TEAEs with onset within 28 days/7 days after study treatment by Dose Number, CTCAE Grade, SOC and PT
- Serious TEAEs by Dose Number, SOC and PT
- TEAEs, TEAEs with onset within 28 days/7 days after study treatment by Dose Number, Relationship to IP and EP, SOC and PT
- Serious TEAEs, serious TEAEs with onset within 28 days/7 days after study treatment by Dose Number, Relationship to IP and EP, SOC and PT
- Grade >= 3 TEAEs, Grade >= 3 TEAEs with onset within 28 days/7 days after study treatment by Dose Number, SOC and PT
- Grade >= 3 TEAEs, Grade >= 3 TEAEs with onset within 28 days/7 days after study treatment by Dose Number, Relationship to IP and EP, SOC and PT
- TEAEs with Action of Study Treatment Held, TEAEs with Action of Study Treatment Held with onset within 28 days/7 days after study treatment by Dose Number, SOC and PT
- TEAEs with Action of Study Treatment Permanently Discontinued, TEAEs with Action of Study Treatment Permanently Discontinued with onset within 28 days/7 days after study treatment by Dose Number, SOC and PT

Additional AE/SAE summary tables may be added as appropriate.

A subject with 2 or more different adverse events within the same level of the MedDRA term and regimen will be counted only once in that level using the most extreme incident (most severe for the intensity analyses, and related for the relationship to study drug analyses). For the AE with missing relationship to drug/procedure will be imputed as related. TEAEs by dose will be counted by the AE onset date not earlier than the date of treatment and earlier than the subsequent treatment for the first dose and second dose, and any AEs with onset date on or later than the third dose will all be counted to the third dose.

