- f At least 34 mL [4 x 8.5 mL yellow (ACD) tubes] whole blood per time point and 8 mL serum per time point at Screening, Day 0 and Week 8 (4 ml serum per time point at Week 15 and 36). A total of at least 68 mL of whole blood and 16 ml serum should be collected prior to dosing on Day 0.
- g At least 51 mL [6 x 8.5 mL yellow (ACD) tubes] whole blood and 4 mL serum should be collected at Week 15;
- h HPV genotyping and Pap smears are performed on the same ThinPrepTM cervical specimen;
- i Request that the subject abstain from sexual activity and refrain from use of douching or vaginal lubricants/medication for a period of 24 hours prior to cervical specimen collection;
- j Collected prior to the ThinPrepTM sample;
- k A photograph of the lesion with at least one attempt should done as follows: Acetic acid should first be applied to the cervix then photographs of the cervix and the associated lesion should be photographed prior to and after biopsies (if applicable) and at all colposcopic examinations; if repeat photographs are sought, they should be done at the next protocol-specified colposcopy visit.
- 1 Screening colposcopy is optional if adequate colposcopy was performed upon collection of initial biopsy;
- m Screening biopsy of the lesion should be collected as Paraffin-embedded cervical tissue, fresh cervical tissue, or H&E slides. Tissue to be analyzed for evidence of histopathologic regression will be obtained at Week 36 visit either by excision (e.g. LEEP, LLETZ, CKC) or by 4 Quadrant Biopsy or 4 Quadrant Biopsy with ECC based upon the assessment at Week 28 of cytology, HR HPV status, and colposcopic findings (See Tables 4 and 5);

- n Slides from biopsy and/or excised tissue must be reviewed by the PAC and residual cervical tissue from screening and/or Week 36 specimen(s) (paraffin blocks or unstained slides) may be used for immunohistochemistry (IHC) and HPV testing;
- o To be collected only if subject consents for intra-anal sample collection
- p One or both PRO questionnaires (i.e. SF-36 and EQ-5D-5L) will be completed by subjects enrolled in USA, Canada, Mexico, Germany and UK at multiple visits during the study. Additional quality of life questions will be asked at the Week 40 phone call. Refer to Section 6.8 for details
- q Activities at 8 to 14 days Post-Dose 3 phone call may be done at Week 15 if timing overlaps.

PPD Biostatistics and Programming

Statistical Analysis Plan (SAP) Client Approval Form

Client:	Inovio					

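### The whole-study adverse-event risk differences include events from a Week 36 procedure that depends on response, and no planned interval covers Weeks 16 to 36 without them

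*SAP*

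**What the plan says.** - **Comparisons between arms.** SAP 9.1.2 gives risk differences with Miettinen-Nurminen 95% intervals for SOC and PT terms. The 28-day window comes first, then the 7-day window, then a comparison "for adverse events during the study after any dose". The section warns that so many intervals need cautious reading.
- **Length of follow-up.** SAP 3.2.2, item 1, follows adverse events through Week 88.
- **What counts.** SAP 9.1 defines a treatment-emergent event as "any event temporally associated with the use of a product whether or not considered related to the use of the product". It sets no end date and does not separate procedure events. In the by-dose tables, "any AEs with onset date on or later than the third dose will all be counted to the third dose".
- **The procedure.** Under SAP 13.1, footnote m, Week 36 tissue is obtained by excision or by four-quadrant biopsy, with or without endocervical curettage. The choice is "based upon the assessment at Week 28 of cytology, HR HPV status, and colposcopic findings". The detailed rule is in tables of the protocol, which is not at hand.
- **A related provision.** SAP 8.4 summarises patient-reported outcomes after Week 36 separately for women with and without excision. SAP section 9 has no counterpart for adverse events.

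**The concern.** Cytology, HPV status and colposcopy at Week 28 are measured after randomisation, and an effective product should change them. If it does, fewer women on VGX-3100 than on placebo go on to excision. Pain, bleeding, discharge or infection after excision would then fall more often on placebo, and the whole-study comparison counts them with everything else.

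Secondary objective 1 (SAP 2.2) concerns the safety and tolerability of VGX-3100 given intramuscularly with electroporation. For the terms that surgery can cause, the whole-study risk difference combines two things: any harm from product and device, and harm from surgery avoided. The two shorter comparisons do not help after about Week 16. A product-related excess arising between Weeks 16 and 36 would therefore appear in an interval only after being mixed with procedure events.

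**Working it through.** **The plan's own figure.** SAP 4.1 gives 198 women, 2:1, for 90% power at 35% vs 14%; SAP 8.1 tests at one-sided 0.025. With pooled variance and no continuity correction, the pooled rate is (0.14 + 2 × 0.35)/3 = 0.28, and

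n(placebo) = [1.960 × √(1.5 × 0.28 × 0.72) + 1.282 × √(0.14 × 0.86 + 0.35 × 0.65/2)]² / 0.21² = 65.4, so 66.

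The total is 66 + 132 = 198, with power 90.3%. The figure reproduces, and 132 and 66 are used below as the arm sizes.

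**Timing.** Doses are at Day 0, Week 4 and Week 12 (SAP 3.3). The 28-day window after the last dose ends at Week 12 + 4 = Week 16. The Week 36 timeframe opens on Day 238 (SAP 8.1): 36 × 7 − 14 = 238. About 20 weeks therefore lie between the end of the short windows and Week 36.

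**Formula.** Let e be the share of an arm that is excised, and qE and qB the risk of a given event after excision and after biopsy. With no direct product effect:

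- risk in an arm = e × qE + (1 − e) × qB
- shift in risk difference = (e on VGX-3100 − e on placebo) × (qE − qB)

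**Excision share (assumed).** If every assumed non-responder and no responder is excised, e is 65% and 86%, a difference of −21 points. If half of the non-responders in each arm are excised, it is −10.5 points.

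**Procedure risks (assumed; the SAP gives none).** The intervals use counts rounded to whole women.

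| qE / qB | VGX-3100 | Placebo | Shift, all non-responders excised | 95% interval at 132/66 | Shift, half excised |
|---|---|---|---|---|---|
| 20% / 5% | 14.75% | 17.9% | −3.2 points | −16.0 to +6.6 | −1.6 |
| 30% / 5% | 21.25% | 26.5% | −5.3 points | −17.9 to +7.5 | −2.6 |
| 50% / 10% | 36.0% | 44.4% | −8.4 points | −22.0 to +6.7 | −4.2 |
| 30% / 30% | 30.0% | 30.0% | 0 | −14.1 to +13.0 | 0 |

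Example, third row: 0.65 × 0.50 + 0.35 × 0.10 = 0.360; 0.86 × 0.50 + 0.14 × 0.10 = 0.444; the difference is −0.21 × 0.40 = −0.084.

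**Could a real excess be hidden?** Suppose the same term has a non-procedure risk of 5% on placebo and 10% on VGX-3100, independent of the procedure, with excision at 65% and 86%. The risk in an arm is 1 − (1 − background) × (1 − procedure risk).

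- 20%/5%: 1 − 0.90 × 0.8525 = 23.3% vs 1 − 0.95 × 0.821 = 22.0%, or +1.3 points
- 30%/5%: 29.1% vs 30.2%, or about −1 point
- 50%/10%: 42.4% vs 47.2%, or −4.8 points

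Under these assumptions, a true 5-point excess shrinks or changes sign.

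**The case against.** The stronger reading is that the safety analysis as a whole is biased and makes VGX-3100 look safer than it is. A reader might infer this, but the documents do not support it.

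- **The comparison is valid for what it measures.** It sets all harm in one arm against all harm in the other. Fewer surgical events on an effective product are a real consequence of treatment. The result misleads only if read as direct toxicity, and SAP 9.1.2 does not ask for that reading. This stands.
- **The shift is conditional and local.** It needs a working product and a higher risk after excision than after biopsy. It touches procedure-type terms and totals containing them. This stands.
- **The 7- and 28-day comparisons are clean.** They end about 20 weeks before Week 36. This stands, but it leaves Weeks 16 to 36 uncovered.
- **Attribution is partly handled elsewhere.** SAP 9.1 plans treatment-emergent events by relationship to product and electroporation, without limit to the short windows. These tables help, but they give counts and percentages rather than risk differences, and they rest on causality judgement.
- **The sizes lean high.** The 65% and 86% treat every failure as excised, yet the assumed rates count about 10% missing data as failures (SAP 4.1), and women who are only HPV-positive also fail. The assumed risks are better read as risks of any procedure event; a single preferred term would shift less. Every interval in the table includes zero, and the SAP attaches no decision to them.
- **The protocol may remove much of it.** It may limit which expected procedure effects are recorded as adverse events. This cannot be checked here.

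**Conclusion.** The point holds in a limited form. The whole-study risk differences include events from a Week 36 procedure whose type depends on response, and the SAP neither labels nor separates them. Read as toxicity of product and device, the differences for procedure-type terms would shift in favour of VGX-3100 by about 3 to 8 points if all assumed non-responders are excised and the excess risk of excision is 15 to 40 points. The shift is about 1.6 to 4.2 points if half are excised, and zero if the two procedures carry equal risk. These sizes rest on the SAP's 35% and 14% response rates, the same excised fraction of non-responders in both arms, and procedure risks that are pure assumption. The gap that remains is specific: no planned interval covers about Weeks 16 to 36 free of Week 36 procedure events.

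**What to change.** 1. Add to SAP 9.1.2 a supportive comparison of adverse events with onset Day 1 through Day 237, by the same Miettinen-Nurminen method and on the same safety population and arms as the other three. It keeps the comparison between randomised groups (SAP 4.3.4 groups women by treatment received, which differs only where dosing departed from assignment). It uses the SAP's own Day 238 boundary.
2. State beside it that it may still contain events from any biopsy or excision done before Day 238. SAP 8.1 allows for such procedures, and they may also depend on response.
3. Keep the Week 88 comparison, labelled as including effects of the Week 36 procedure.
4. Optionally, tabulate later events by arm and by excision or biopsy, as SAP 8.4 does by excision for patient-reported outcomes. This must be descriptive only, because those groups are formed after randomisation.

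The cost is a few lines of SAP text and one more run of an existing table, with no change to data collection. The downside is one more set of safety intervals to read.

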9.2. Clinical Laboratory Evaluations

Laboratory evaluations (including hematology, serum chemistry, and urinalysis) will be collected at the screening visit (within 30 days prior to Day 1), and a summary of screening information will be provided by treatment arm and by total.

9.3. Vital Sign Measurements

Vital sign data will be summarized at each visit by treatment arm. Changes from baseline to each scheduled post-baseline visit will be presented as well.

9.4. Physical Examination

During physical examinations, body systems will be assessed as normal, abnormal, or not examined at each scheduled visit, and the percentage of subjects with abnormal physical examination findings at each time point will be summarized by body system and by treatment arm.

9.5. Electrocardiogram

A standard 12-lead electrocardiogram (ECG) will be performed at Screening after the subject has been in a supine position for 10 to 15 minutes. ECG results will be summarized by treatment arm and by total, for interpretation results including Normal, Abnormal Not Clinically Significant, Abnormal Clinically Significant, and Not Done.

10. Interim Analysis

For reasons of futility (early evidence of poor efficacy of VGX-3100) or safety issues, the DSMB could recommend stopping enrollment at any time; no formal interim analysis will be performed for this purpose. The type I error of 0.05 will not be adjusted for possible early stopping due to futility.

Group-level unblinded (VGX-3100, Placebo) summaries and analyses of efficacy will be produced once the primary endpoint Week 36 visit data are completed for all subjects; subject-level blinding will be maintained. Long-term follow-up data will continue to be collected for all subjects with remaining visits through the final Week 88 visit. The summaries and analyses will allow the Sponsor to have results with respect to the primary endpoint and all other efficacy endpoints corresponding to the cervix and the Week 36 visit on which to make decisions regarding the VGX-3100 program, while still gathering secondary and exploratory endpoint and safety data through the final Week 88 visit. The planned set of summaries and analyses is comprised of a) the primary composite endpoint of histopathologic regression and virologic clearance, b) the secondary endpoint of histopathologic regression, c) the secondary endpoint of virologic clearance, d) the secondary composite endpoint of histopathologic regression to normal and virologic clearance, e) the secondary endpoint of histopathologic regression to normal, and f) the secondary endpoint of histopathologic non-progression. None of these summaries or analyses will be provided if the total count of subjects who experience the event of interest is greater than 0 and the count for any treatment group relative to this total count is less than 3% for a given summary/analysis. Also, items a) through f) are planned to be produced in the order in which they are listed, but as there are intersecting endpoints among these items, items among b) through f) will not be produced if the difference in total count of subjects who experience the event of interest is greater than 0 and the count for any treatment group is 0, relative to any preceding item in the set. The group-level unblinded (VGX-3100, Placebo) production of the summaries and analyses will not include anyone directly involved with the trial or any additional unblinded personnel; only the external Contract Research Organization (CRO), PPD, which has already been providing unblinded summaries for the Data Safety Monitoring Board, will be utilized. Thus, the trial will remain blinded with respect to subject treatment assignment throughout the trial. The type I error of 0.05 will not be adjusted for this procedure.

11. Changes in the Planned Analysis

The following changes from the protocol have been made in the planned analysis:

- In section 4.3.3, additional analyses on the PP population are added to serve as sensitivity analyses regarding early intervention. These are not specified in protocol.
- In Table 2, for the clearance from non-cervical anatomic locations endpoint, the table states that excision or biopsies performed on or after Day 1 but before the Week 36 timeframe will not be used to define responder/non-responder, as these procedures should not impact the Week 36 timeframe results for this endpoint. This was not specified in Table 11 of the protocol.

12. References

- 1. A Prospective, Randomized, Double-Blind, Placebo-Controlled Phase 3 Study of VGX-3100 Delivered Intramuscularly Followed by Electroporation with Cellectra™ 5PSP for the Treatment of HPV-16 And/Or HPV-18 Related High Grade Squamous Intraepithelial Lesion (HSIL) of the Cervix, Version 3.0, 23 September 2016.
- 2. Centers for Disease C, Prevention. Human papillomavirus-associated cancers United States, 2004-2008. MMWR Morb Mortal Wkly Rep 2012,61:258-261.
- 3. Future II Study Group. Supplementary Material: Quadrivalent vaccine against human papillomavirus to prevent high-grade cervical lesions. N Engl J Med 2007,356:1915-1927.

13. Appendices

